#### Baseline SARS-CoV-2 Status for Each Part

- **Pre-Dose 1 SARS-CoV-2 status for long-term analysis** is determined by using virologic and serologic evidence of SARS-CoV-2 infection on or before the date of first dose of mRNA-1273 (the first dose of mRNA-1273 in Part 1A for subject who receive mRNA-1273 in Part 1A or the first dose of mRNA-1273 in Part 1B for subjects who receive Placebo in Part 1A).

Negative SARS-CoV-2 status for long-term analysis is defined as a most recent negative RT-PCR test for SARS-CoV-2 and a most recent negative serology test based on bAb specific to SARS-CoV-2 nucleocapsid (as measured by *Roche Elecsys Anti-SARS-CoV-2 assay*) on or before the date of the first dose of mRNA-1273.

Positive SARS-CoV-2 status for long-term analysis is defined as a most recent positive RT-PCR test for SARS-CoV-2 at the date of the first mRNA-1273 dose, and/or a most recent positive serology test based on bAb specific to SARS-CoV-2

nucleocapsid (as measured by *Roche Elecsys Anti-SARS-CoV-2 assay*) on or before the date of the first dose of mRNA-1273.

- **Pre-booster SARS-CoV-2 Status**

**Pre-booster SARS-CoV-2 status** for Part 1C-1 and Part 1C-2 is determined by using virologic and serologic evidence of SARS-CoV-2 infection on or before the date of booster dose (BD-Day 1).

Pre-booster positive SARS-CoV-2 status is defined as a positive RT-PCR test for SARS-CoV-2, and/or a positive serology test based on bAb specific to SARS-CoV-2 nucleocapsid (as measured by *Roche Elecsys Anti-SARS-CoV-2 assay*) on or before BD-Day 1.

Pre-booster negative status is defined as a negative RT-PCR test for SARS-CoV-2 and a negative serology test based on bAb specific to SARS-CoV-2 nucleocapsid (as measured by *Roche Elecsys Anti-SARS-CoV-2 assay*) on or before BD-Day 1.

- **Baseline SARS-CoV-2 status for Part 2 and Part 3** is defined using the same approach as Part 1A.

**Study day relative to the first** injection in Part 1B or Part 2 or Part 3 will be calculated as below:

- a) study day prior to the first injection will be calculated as: date of assessment/event – date of the first injection in Part 1B or Part 2 or Part 3;
- b) study day on or after the date of the first injection will be calculated as: date of assessment/event – date of the first injection in Part 1B or Part 2 or Part 3 + 1;

**Study day relative to the booster** injection in Part 1C-1 or Part 1C-2 or Part 2 (for participants who receive booster dose) will be calculated as below:

- a) study day prior to the booster dose will be calculated as: date of assessment/event – date of the booster injection;
- b) study day on or after the date of the booster dose will be calculated as: date of assessment/event – date of the booster injection + 1;

**Study day relative to the most recent** injection will be calculated as below:

- a) study day on or after the date of the first injection (if applicable) but before the second injection (if applicable) will be calculated as: date of assessment/event – date of the first injection + 1;
- b) study day on or after the date of the second injection (if applicable) but before the booster injection (if applicable) will be calculated as: date of assessment/event – date of the second injection + 1;
- c) study day on or after the date of booster dose in Part 1C-1 (if applicable), Part 1C-2 or Part 2 (for participants who receive booster dose) will be calculated as: date of assessment/event – date of the booster injection + 1;  
if study day is on the same day as the injection, date and time will be compared with the injection date and time.

**For calculation regarding antibody levels/titers**, antibody values reported as below LLOQ will be replaced by  $0.5 \times \text{LLOQ}$ . Values that are greater than the upper limit of quantification (ULOQ) and without actual values reported (eg, '>xxx') will be converted to the ULOQ. Values that are greater than the ULOQ and with actual values reported will not be imputed (i.e. actual values will be used). Missing results will not be imputed.

The following **analysis periods for safety analyses** will be used as applicable for specific subjects cohort in this study:

- Up to 28 days after vaccination: this stage starts at the day of each vaccination and continue through the earliest date of (the day of each vaccination and 27 subsequent days, next vaccination [if applicable]). This analysis period will be used as the primary analysis period for safety analyses including unsolicited AE, except for solicited AR, unless specified otherwise.
- Overall period or throughout the study: this analysis period starts at the first injection on Day 1 and continues through the earliest date of (study completion, discontinuation from the study, or death).
- After First Injection and Before Second Injection (Part 3): this analysis period starts at the first injection on Day 1 and continues through the earliest date of (Second injection, study completion, discontinuation from the study, or death).

- After Second Injection (Part 3): this analysis period starts at the second injection on Day 181 and continues through the earliest date of (study completion, discontinuation from the study, or death).

**Unscheduled visits:** Unscheduled visit measurements will be included in analysis as follows:

- In scheduled visit windows per specified visit windowing rules.
- In the derivation of baseline/last on-treatment measurements.
- In the derivation of maximum/minimum on-treatment values and maximum/minimum change from baseline values for safety analyses.
- In individual subject data listings as appropriate.

**Visit windowing rules:** The analysis visit windows for protocol-defined visits are provided in [Appendix B](#).

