For assessments that will be collected at study visits (e.g. vital sign), if a subject receives two injections, this stage starts from the day after Day 57 visit and continues until the earliest date of (unblinding, non-study COVID-19 vaccine use, first injection in Part 1B, injection in Part 1C-1, study completion, discontinuation from the study, or death); if a subject receives first injection only, this stage starts from the day after Day 29 visit and continues until the earliest date of (unblinding, non-study COVID-19 vaccine use, first injection in Part 1B, injection in Part 1C-1, study completion, discontinuation from the study, or death).

- Overall period: this analysis period starts at the first injection on Day 1 and continues through the earliest date of (unblinding, non-study COVID-19 vaccine use, first injection in Part 1B, injection in Part 1C-1, study completion, discontinuation from the study, or death).

**Unscheduled visits:** Unscheduled visit measurements will be included in analysis as follows:

- In scheduled visit windows per specified visit windowing rules.
- In the derivation of baseline/last on-treatment measurements.
- In the derivation of maximum/minimum on-treatment values and maximum/minimum change from baseline values for safety analyses.
- In individual subject data listings as appropriate.

**Visit windowing rules:** The analysis visit windows for protocol-defined visits are provided in [Appendix B](#).

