#### **Analysis Periods**

The following analysis periods and treatment groups will be used for the Blinded Phase Analysis.

- Blinded Phase:

Cohort	Category	Start Date of Blinded Phase	End Date of Blinded Phase
mRNA-1273	Safety	Date of First Dose	Earliest date of unblinding (non-inclusive), non-study COVID-19 vaccination, first injection in Part 1B, injection in Part 1C-1, study discontinuation, study completion, death, or data cutoff
Placebo			
mRNA-1273	Efficacy/Immunogenicity	Randomization Date	Earliest date of unblinding (inclusive), non-study COVID-19 vaccination date, first injection in Part 1B, injection in Part 1C-1, study discontinuation, study completion, death, or data cutoff
Placebo			

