## 9.6. Appendix F Schedule of Assessments (Part 1B, Open-label Observational Phase for Subjects Who Previously Received Placebo)

	Visit Number	7	8	9	10	11
	Type of Visit	C	C	C	SC 	C
Study Visit Day	(~D209/ Participant Decision Visit) OL-D1	OL-D29	OL-D57 	OL-D113	OL-D178 	
Window Allowance (Days)	-56/+56 	-3/+7	±14	±3	±14	
Days Since Most Recent Injection	0	28	28	84	84	149
Informed consent form	These assessments are already performed as part of the regular D209 Visit.		X			X
Blood for vaccine immunogenicity			X			
Nasopharyngeal or nasal swab sample for SARS-CoV- 2 			X			
Physical examination including vital signs 						X
Pregnancy testing						
Study injection (including 30-minute postdosing observation period)	X	X				
Informed consent for BD				X 		
Recording of MAAEs and concomitant medications relevant to or for the treatment of the MAAE 	X	X	X	X	X	X
Recording of SAEs and concomitant medications relevant to or for the treatment of the SAE 	X	X	X	X	X	X

	Visit Number	7	8	9	10	11
Type of Visit	C	C	C	SC 	C	
Study Visit Day	(~D209/ Participant Decision Visit) OL-D1	OL-D29	OL-D57 	OL-D113	OL-D178 	
Window Allowance (Days)	-56/+56 	-3/+7	±14	±3	±14	
Days Since Most Recent Injection	0	28	28	84	149	
Recording of AESI	X	X	X	X	X	
Recording of concomitant medications and nonstudy vaccinations 	X	X	X	X	X	
Surveillance for COVID-19/ Unscheduled visit	visit  /	X	X	X	X	
Study completion (for Part 1B)					X	

Abbreviations: AE = adverse event; AESI = adverse event of special interest; C = clinic visit; COVID-19 = coronavirus disease 2019; D = Day; M = month; MAAE = medically attended AE; NP = nasopharyngeal; OL = open-label; PCR = polymerase chain reaction; RT-PCR = reverse transcriptase polymerase chain reaction; SAE = serious adverse event; SARS-CoV-2 = Severe Acute Respiratory Syndrome coronavirus 2; SC = safety (telephone) call.

1. The Participant Decision Visit may be performed over multiple visits. Once the Participant Decision Visit has been initiated, all assessments must be completed within a 7-day period.
2. After the OL-D57 visit, Part 1B participants who choose to receive BD will have one additional safety call at OL-D113 prior to entering Part 1C-1..

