### Analysis periods

The following analysis periods and treatment groups will be used for Long-term Analysis (including Part 1B) and Part 1C-1 Homologous Booster Dose Analysis.

- Long-term Analysis (Part 1A plus Part 1B)

Cohort	Category	Start Date	End Date
mRNA-1273	Safety	Date of First Dose of mRNA-1273	Earliest date of booster dose, study discontinuation, study completion, death, or data cutoff
Placebo - mRNA-1273			
mRNA-1273	Efficacy/ Immunogenicity	Date of First Dose of mRNA-1273	Earliest date of booster dose (inclusive), study discontinuation, study completion, death, or data cutoff
Placebo - mRNA-1273			

Long-term analysis of incidence rate will also be performed for the entire study period after the first dose of mRNA-1273 regardless of booster dose.

- Part 1C-1 Homologous Booster Dose Analysis

Cohort	Category	Start	End
mRNA-1273 - Booster	Safety	Date of Booster Dose	Earliest date of study discontinuation, study completion, death, or data cutoff
Placebo - mRNA-1273 - Booster			

mRNA-1273 - Booster	Efficacy/ Immunogenicity	Date of Booster Dose (considered as pre- booster data)	Earliest date of study discontinuation, study completion, death, or data cutoff
Placebo - mRNA-1273 - Booster			

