#### 6.3.1. Adverse Events

A treatment-emergent AE (TEAE) is defined as any event occurring during the study not before exposure to study vaccine or any event already present that worsens after exposure to study vaccine. [Note: worsening of a pre-existing condition after vaccination will be reported as a new AE.]

Adverse events will also be evaluated by the investigator for the coexistence of MAAE which is defined as an AE that leads to an unscheduled visit to a healthcare practitioner.

Unsolicited AEs will be coded by PT and SOC using MedDRA and summarized by vaccination group, and stage (up to 28 days after any vaccination and overall stage [Long-term analysis, Part 2 primary series phase], up to 28 days after booster dose and overall stage [Part 1C-1, Part 1C-2], up to 28 days after each vaccination, after first injection and before second injection, after second injection, and throughout the study [Part 3]; see [Section 6.1](#) for definitions of vaccination group and stage).

All summary tables (except for the overall summary of AEs) for unsolicited AEs will be presented by SOC and PT for TEAEs with counts of subjects included. SOC will be displayed in internationally agreed order. PT will be displayed in descending order of frequency of mRNA-1273 (except Part 3) or mRNA-1273.222 group (Part 3) and then alphabetically within SOC. When summarizing the number and percentage of subjects with an event, subjects with multiple occurrences of the same AE or a continuing AE will be counted once. Subjects will be presented according to the highest severity (the strongest

relationship) in the summaries by severity (of related AEs), if subjects reported multiple events under the same SOC and/or PT.

Percentages will be based upon the number of subjects in the Safety Set for specified analysis within each vaccination group except summary after second injection in Part 3, which will be based on the Second Injection Safety Set.

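### The two Part 3 safety periods both contain the Dose 2 day, and the next-dose boundary is inconsistent in the Part 1A overall period and unstated in the long-term safety row

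*SAP*

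**What the plan says.** **Part 3** (SAP for Parts 1B, 1C, 2 and 3, Section 6.1, analysis periods for safety analyses). The period labelled "After First Injection and Before Second Injection (Part 3" begins at the first injection on Day 1 and "continues through the earliest date of (Second injection, study completion, discontinuation from the study, or death". For the following period, "this analysis period starts at the second injection on Day 181 and continues through the earliest date of" study completion, discontinuation or death. Section 6.3.1 tabulates unsolicited events separately for both periods, with percentages for the later one "which will be based on the Second Injection Safety Set".

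**Blinded phase** (SAP for Part 1A, Section 6.1). The overall period "continues through the earliest date of (unblinding, non-study COVID-19 vaccine use, first injection in Part 1B, injection in Part 1C-1" and the remaining end events, with no statement on whether the end day counts. The Analysis Periods table in the same section ends blinded-phase safety at "Earliest date of unblinding (non-inclusive), non-study COVID-19 vaccination, first injection in Part 1B, injection in Part 1C-1" and so on; only unblinding carries a tag. Section 6.3.1 of that SAP sends unsolicited events to the 28-day stage and the overall stage. Appendix F heads the first open-label dosing column "D209/ Participant Decision Visit) OL-D1".

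**Booster** (SAP for Parts 1B, 1C, 2 and 3, Section 6.1, Analysis periods). Long-term safety ends at "Earliest date of booster dose, study discontinuation, study completion, death, or data cutoff". The booster safety period starts on the date of the booster. The efficacy and immunogenicity row of the long-term table is tagged as including the booster day; the safety row has no tag.

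**Same-day rule.** Both SAPs compare date and time with the injection when they fall on the same day, but only under study day relative to the most recent injection.

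**The concern.** A safety period named as preceding a dose should not contain events that follow that dose. Reactions that come on quickly begin on the day of dosing, so this boundary day matters more than most. If consecutive periods share it and no rule separates them, one event appears in two tables, and in Part 3 on two denominators. If two definitions of the same phase treat the day differently, the count depends on which one the programmer follows. Where events are few, as with serious events or events of special interest, a single case can change a cell.

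**Working it through.** The SAP gives no figure to reproduce. The check counts the calendar days that two consecutive periods share:

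overlap = max(0, min(end of first, end of second) − max(start of first, start of second) + 1)

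**1. Part 3.** Let d be the Dose 2 day and E any later end day. The cases are d = 181 (nominal), 188 (the +7 window) and 202 (the +21 pandemic extension), all from Appendix K of the SAP for Part 1A.
- As worded, with the end day included: the periods are [1, d] and [d, E]. Overlap = d − d + 1 = 1 day for each d. At d = 181: 181 − 181 + 1 = 1.
- With the first period ending the day before: [1, d − 1] and [d, E]. Overlap = (d − 1) − d + 1 = 0 days for each d.

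The SAP's own usage supports including the end day. In the same list, the 28-day stage runs through the day of vaccination and the 27 days after it, which gives 1 + 27 = 28 days only if the last day counts. The same end list also contains death, and excluding that day would drop events that start on it.

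**2. 28-day stage.** The first period is [1, min(28, d)] and the second is [d, d + 27].
- d = 29: 28 − 29 + 1 = 0 days.
- d = 36: 28 − 36 + 1 = −7, so 0 days.
- d = 50: 28 − 50 + 1 = −21, so 0 days.
- d = 181 or later: 0 days.
- d = 28: 28 − 28 + 1 = 1 day.
- d = 26 (the Part 1B second dose at the early edge of its −3 window, Appendix F): 26 − 26 + 1 = 1 day.

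This stage overlaps only when the next dose comes by Day 28.

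**3. Crossover from placebo.** Let U be the unblinding day and C the crossover dose day. Unblinding comes first (SAP for Part 1A, Section 4.1.1.2), so C ≥ U. Appendix F lets the decision visit be spread over up to 7 days, so the two may coincide or differ. The date pairs below are illustrative.
- Blinded-phase table, unblinding day excluded: the last placebo safety day is U − 1. For U/C = 209/209, 203/209 and 209/216 it is 208, 202 and 208. None contains C.
- Overall period, end day included: the last day is min(U, C). For the same pairs it is 209, 203 and 209. Only 209/209 contains C.

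The two definitions therefore differ on whether the crossover dose day is included only when unblinding and dosing fall on the same day.

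**4. Booster.** The long-term safety period ends at the booster date and the booster safety period starts on it. The overlap is 1 day if the end is inclusive and 0 if it is exclusive; the safety row does not say which. Two places point to exclusive: the neighbouring row is expressly tagged as inclusive, and Section 6.6 of the SAP for Part 1A limits the long-term analysis to data before the booster.

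**The case against.** The strongest reply is that the intent is plain and little depends on it. The Part 3 label itself says that the period precedes Dose 2. The blinded-phase table is the specific rule for that phase and keeps the crossover day out of placebo. The long-term analysis is scoped to data before the booster. The reactions most expected on dosing day are solicited and tabulated by injection. The primary period for unsolicited events is the 28-day stage. Part 3 has one vaccine group and its primary safety objective now concerns one dose, so no between-group contrast is blurred.

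Most of this stands, and it sets the size of the point. It does not remove it. A label does not override the period definition beneath it, and in Part 3 the two contradict each other. The date-and-time comparison would settle the matter but is not written for periods. In Part 1A the adverse-event section refers to the overall stage, which is the name of the looser definition. The table tags only unblinding, so a non-study vaccination taken while still blinded has no stated rule.

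A reader might go further and infer that dosing-day events are moved out of the post-dose tables, that placebo is charged with vaccine reactions, or that booster-day events enter the primary-series table. The SAP does not support these readings. A Part 3 Dose 2-day event always remains in the post-Dose 2 table. The placebo effect requires the overall bullet to be read inclusively and unblinding and dosing to share a day. The booster row is an unstated boundary, not a defined overlap.

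**Conclusion.** The point holds for Part 3: as worded, an unsolicited event starting on the Dose 2 day is counted in both periods, contrary to the first period's label. The Part 1A overall period and the blinded-phase table conflict and must be reconciled. The long-term safety row lacks a tag, and the surrounding text suggests that exclusion is intended.

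The effect is one calendar day of unsolicited events per boundary, in secondary descriptive periods. Solicited reactions are unaffected, as is the 28-day stage at nominal dosing intervals. The Part 3 result assumes that the end day is included, which the SAP's own usage supports. The number of events cannot be derived: the document gives neither a dosing-day event rate nor the number who received Dose 2 in Part 3. This is a minor correction, but worth making because the Part 3 rule as stated yields wrong counts.

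**What to change.** - **Part 3, Section 6.1 (SAP for Parts 1B, 1C, 2 and 3):** end the first period before the second injection, meaning the day before, or before the recorded dose time on that day.
- **Overall period, Section 6.1 (SAP for Part 1A):** adopt the non-inclusive rule of the blinded-phase table, and in both places apply it also to the first Part 1B injection, the Part 1C-1 injection and non-study COVID-19 vaccination.
- **Long-term safety row, Section 6.1 (SAP for Parts 1B, 1C, 2 and 3):** tag the booster dose as non-inclusive.
- **Both SAPs:** state that the date-and-time comparison now written for study day also governs assignment of events to safety periods.
- Leave the efficacy and immunogenicity rows inclusive.

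Ending each period the day before the next dose brings the overlap to 0 days in every case checked above. The cost is a few words in Section 6.1 of each SAP and a small change to the period-flag programming. No data collection or clinical procedure changes.

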**Incomplete/missing data:**

- Imputation rules for missing prior/concomitant medications, non-study vaccinations and procedures are provided in [Appendix C](#).
- Imputation rules for missing AE dates are provided in [Appendix D](#).
- For laboratory assessments, if majority of results are indefinite, imputation of these values will be considered. If the laboratory results are reported as below the LLOQ (e.g., <0.1), the numeric values will be imputed by  $0.5 \times \text{LLOQ}$  in the summary. If the laboratory results are reported as greater than the ULOQ (e.g., “>3000”), the numeric values will be imputed by ULOQ in the summary.
- Other incomplete/missing data will not be imputed, unless specified otherwise.

**Treatment groups:**

The following vaccination groups will be used for summary purposes:

- Long-term Analysis (Part 1A plus Part 1B):
  - mRNA-1273: Participants from Part 1A mRNA-1273 group
  - Placebo - mRNA-1273: Participants from Part 1A placebo group who cross over and receive mRNA-1273 in Part 1B

- Part 1C-1 Homologous Booster Dose Analysis:
  - mRNA-1273 - Booster: Participants from Part 1A mRNA-1273 group who received booster dose in Part 1C-1
  - Placebo - mRNA-1273 - Booster: Participants from Part 1A placebo group who crossed over to receive mRNA-1273 in Part 1B, and received booster dose in Part 1C-1.
- Part 1C-2 Heterologous Booster Dose Analysis: Heterologous Booster
- Part 2: mRNA-1273 50 µg
- Part 3: mRNA-1273.222 50 µg

### Analysis periods

The following analysis periods and treatment groups will be used for Long-term Analysis (including Part 1B) and Part 1C-1 Homologous Booster Dose Analysis.

- Long-term Analysis (Part 1A plus Part 1B)

Cohort	Category	Start Date	End Date
mRNA-1273	Safety	Date of First Dose of mRNA-1273	Earliest date of booster dose, study discontinuation, study completion, death, or data cutoff
Placebo - mRNA-1273			
mRNA-1273	Efficacy/ Immunogenicity	Date of First Dose of mRNA-1273	Earliest date of booster dose (inclusive), study discontinuation, study completion, death, or data cutoff
Placebo - mRNA-1273			

Long-term analysis of incidence rate will also be performed for the entire study period after the first dose of mRNA-1273 regardless of booster dose.

- Part 1C-1 Homologous Booster Dose Analysis

Cohort	Category	Start	End
mRNA-1273 - Booster	Safety	Date of Booster Dose	Earliest date of study discontinuation, study completion, death, or data cutoff
Placebo - mRNA-1273 - Booster			

mRNA-1273 - Booster	Efficacy/ Immunogenicity	Date of Booster Dose (considered as pre- booster data)	Earliest date of study discontinuation, study completion, death, or data cutoff
Placebo - mRNA-1273 - Booster			

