#### **4.1.2. Part 2 Study Design**

Part 2 is an open-label design. The study will evaluate the safety, reactogenicity, and effectiveness of a 50 µg primary series of mRNA-1273 SARS-CoV-2 vaccine in healthy adolescents 12 to < 18 years of age.

[figure not shown]
The study schema arms and major study events for Part 2 participants who receive the booster dose is illustrated in [Figure 5](#) and the SoA is located in [Appendix I](#). The study schema for Part 2 participants who do not receive the booster dose is illustrated in [Figure 6](#) and the SoA is located in [Appendix J](#).

Participants who receive the booster dose of mRNA-1273 in Part 2 will be in the study approximately 17 months, which includes 1 week for screening (Day -7 to Day 1), 4 months for dosing (on Day 1, Day 29, and Day 149), and 12 months of follow-up after the booster dose. Participants who do not receive the booster dose of Participants who received mRNA-1273 in Part 2 will be in the study approximately 12 months, which includes 1

week for Screening (Day -7 to Day 1), 1 months for dosing (on Day 1, Day 29), and 12 months of follow-up after Dose 2.

[figure not shown]
Note: Due to emergence of a more divergent variant of concern (ie, Omicron), Study Part 3 was initiated to replace the investigative product mRNA-1273 with a bivalent vaccine mRNA-1273.222. This amendment aimed to assess primary series of 50 µg bivalent mRNA-1273.222 in Part 3 of the study. As a result of this amendment, Part 2 enrollment was discontinued effective 16 August 2022. The booster administration (Protocol Amendment 4) was also removed and was reflected in the Protocol Amendment 5 SoA. Participants enrolled in Part 2 who have received the primary series or third (booster) dose in this study and would like to receive the bivalent COVID-19 vaccine, can receive it outside of Study P203. Participants who receive the updated bivalent COVID-19 vaccine may remain in the P203 study after receipt of the nonstudy vaccine. However, sites must report this as concomitant medication.

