### **Per-protocol (PP) Immunogenicity Subset (Part 3)**

Per-Protocol (PP) Immunogenicity Subset (Part 3) consists of all participants in Immunogenicity Subset (Part 3) who meet all the following criteria:

- a) Received planned doses of study vaccination per schedule
- b) Had Day 29 Ab assessment for the analysis endpoint
- c) Had no major protocol deviations that impact key or critical data
- d) Not receive off-study COVID-19 vaccination prior to Day 29 visit

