### **6.5.2. Analysis Method**

The number and percentage of subjects who had an event will be summarized in the mITT1 Set for the long-term analysis and Part 1C-1 booster dose phase analysis, and FAS for Part 1C-2, Part 2 and Part 3 analysis.

The incidence rate will be provided by vaccination group if applicable, calculated as the number of cases divided by the total person-time. The 95% CI of the incidence rate will be calculated using the exact method (Poisson distribution) and adjusted by person-time.

Person-time is defined as the total time from date of the 1st dose of each part to the date of event, dose date in next part, last date of study participation, censoring time, or efficacy data cutoff date, whichever is earlier.

Incidence rate will also be analyzed by time period or by calendar month as applicable.

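### Off-study COVID-19 vaccination ends the analysis periods in the Part 1A SAP, but the SAP for Parts 1B, 1C, 2 and 3 sets no such limit, so exploratory late titers and incidence rates can include re-vaccinated participants.

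*SAP*

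**What the plan says.** **Part 1A SAP.** The Analysis Periods table in Section 6.1 ends the blinded-phase efficacy/immunogenicity period at "Earliest date of unblinding (inclusive), non-study COVID-19 vaccination date, first injection in Part 1B, injection in Part 1C-1", followed by the usual study-exit events. The safety row of that table also lists non-study vaccination, as does the follow-up safety period. The overall safety period "continues through the earliest date of (unblinding, non-study COVID-19 vaccine use, first injection in Part 1B, injection in Part 1C-1" or a study-exit event.

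**SAP for Parts 1B, 1C, 2 and 3.** The Section 6.1 tables cover only two analyses. The long-term efficacy/immunogenicity row ends at "Earliest date of booster dose (inclusive), study discontinuation, study completion, death, or data cutoff". Both Part 1C-1 rows end at "Earliest date of study discontinuation, study completion, death, or data cutoff". The overall safety period in the same section stops only at study completion, discontinuation or death. No such table is given for Parts 1C-2, 2 or 3.

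For incidence, Section 6.5.2 states: "Person-time is defined as the total time from date of the 1st dose of each part to the date of event". It then adds the dose date in the next part, last participation, censoring time and data cutoff. Censoring time is not defined.

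Off-study vaccination is a criterion only in some per-protocol immunogenicity subsets of Section 5.3. For Part 3 it reads "Not receive off-study COVID-19 vaccination prior to Day 29 visit". Parts 1C-1 and 1C-2 have the equivalent up to BD-Day 29. The long-term and Part 2 subsets have none.

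The event is foreseen. The Part 1A SAP, in Section 4.1.2 for Part 2 and likewise in Section 4.1.1.4 for Part 1C-2, says "Participants who receive the updated bivalent COVID-19 vaccine may remain in the P203 study after receipt of the nonstudy vaccine", and asks sites to report it as a concomitant medication.

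**The concern.** The later-parts SAP plans geometric means at BD-Day 181 and BD-Day 361 (Parts 1C-1 and 1C-2), Day 209 and Day 394 (Part 2), and Day 85 and Day 181 (Part 3). Its objectives describe these as persistence of the response to the study dose. A titer drawn after a further dose elsewhere measures something else and would normally push the mean up. In the same way, person-time after such a dose would normally pull the incidence rate down through protection that the study vaccine did not provide.

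The plan already treats a further dose as ending the question when it is given in the study: long-term follow-up stops at the booster, and person-time stops at the dose in the next part. Where it wants an analysis that ignores a later dose, it says so, as for the long-term incidence rate regardless of booster. It says nothing comparable for off-study doses. The choice is left to programming, possibly after data have been seen.

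**Working it through.** The plan states no figure on this point, so the check is a comparison of rules, followed by an illustration of scale.

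**1. Where off-study COVID-19 vaccination acts as a limit**

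| Rule | Part 1A SAP | Later-parts SAP |
|---|---|---|
| Efficacy/immunogenicity end date (6.1) | listed | not listed (long-term, Part 1C-1); no table for Parts 1C-2, 2, 3 |
| Overall safety period (6.1) | listed | not listed |
| Person-time (6.5.2) | not listed; censoring time can draw on the 6.1 table | not listed; censoring time has no listed vaccination end date to draw on |
| PP immunogenicity subset | no separate criterion; the period ends at the event | Parts 1C-1, 1C-2, 3: up to the one-month visit; long-term and Part 2: none |
| Incidence analysis sets | period ends at the event | mITT1 (long-term, 1C-1) and FAS (1C-2, 2, 3): no criterion |

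**2. Overlap.** The long-term mRNA-1273 cohort starts at the first mRNA-1273 dose, which for that cohort falls in Part 1A. Suppose a participant in that cohort is vaccinated elsewhere while still blinded. Time after that date is cut off under the Part 1A table and counted under the long-term table. For this cohort the two rules act on the same data.

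**3. Which results are exposed**

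- Part 1C-2 late titers and Part 2 Day 209/394: exposed, with off-study vaccination explicitly allowed.
- Part 2 Day 57, a descriptive primary timepoint: no explicit exclusion, though the interval is short.
- Part 3 Day 85/181: exposed after Day 29.
- Part 1C-1 BD-Day 181/361: exposed where tested. Section 6.4.1 commits only BD-Day 1 and BD-Day 29 booster-phase samples to testing.
- Incidence rates in all later parts: exposed.
- Long-term Day 57/209 titers: little exposed. Section 6.4.1 draws that subset from people who later took the in-study booster, and the period ends there.
- Part 1C-1 BD-Day 29 and Part 3 Day 29, the tested endpoints: protected by the Section 5.3 criteria. Part 1C-2 BD-Day 29 is protected in the same way.

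**4. Scale, on assumed inputs.** Let q be the share re-vaccinated and r the fold difference in their titers. The geometric mean in Section 6.4 averages log titers, so the log mean shifts by q × log r and the reported mean is multiplied by r^q.

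- q = 5%, r = 2: 2^0.05 = 1.04
- q = 10%, r = 5: 5^0.10 = 1.17
- q = 20%, r = 5: 5^0.20 = 1.38
- q = 30%, r = 10: 10^0.30 = 2.00

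Let w be the share of person-time after off-study vaccination and h the relative hazard in that time. The incidence rate is multiplied by 1 − w(1 − h).

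- w = 5%, h = 0.7: 1 − 0.05 × 0.3 = 0.985
- w = 20%, h = 0.5: 1 − 0.20 × 0.5 = 0.90
- w = 30%, h = 0.3: 1 − 0.30 × 0.7 = 0.79

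None of q, r, w or h is in the documents.

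**The case against.** Several points on the other side are sound. The persistence and incidence endpoints are exploratory, with no test or success criterion. Part 2 is purely descriptive and small. Permission to be vaccinated elsewhere and stay in the study is written only for Parts 1C-2 and 2. The Part 1A person-time definition does not name off-study vaccination either and uses the same term, censoring time. In the later-parts SAP that term could be read to cover the event. A descriptive summary regardless of off-study vaccination is also legitimate if it is labelled as such.

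These points limit the reach of the problem but do not remove it. In Part 1A, censoring time can be read against a table that names the event; the corresponding later-parts table omits it. The major-deviation criterion does not fill the gap, because no stated rule classes off-study vaccination as a deviation, and Parts 1C-2 and 2 allow it with continued participation. No label says that the later-parts analyses are meant to ignore it.

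A reader might infer that the two SAPs contradict each other throughout. The documents do not support that: each states its own scope, and differing end dates for a blinded comparison and for later descriptive follow-up are not in themselves a conflict. The direct clash is confined to blinded-phase time in the long-term mRNA-1273 cohort.

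**Conclusion.** The gap is real and should be fixed, but it does not threaten the study's main conclusions. Following the listed end dates, exploratory late titers and incidence rates can include follow-up after off-study vaccination, chiefly in Parts 1C-2 and 2. Part 2 Day 57 also lacks an explicit exclusion.

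A reader might go further and infer that the noninferiority and superiority results of Parts 1C-1 and 3 are contaminated, or that the late summaries are certain to be. Neither follows. The tested endpoints sit at the one-month visit, where the per-protocol criteria exclude earlier off-study vaccination. The undefined censoring time leaves room for a programmer to stop person-time at the event.

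The direction of bias, upward for titers and downward for incidence, assumes that an off-study dose raises antibody and protects. Its size cannot be derived from the documents. The factors of 1.04 to 2.00 and 0.985 to 0.79 illustrate assumed inputs only, and the extremes need both inputs at their limits.

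**What to change.** In the SAP for Parts 1B, 1C, 2 and 3:

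- Section 6.1: add non-study COVID-19 vaccination to the efficacy/immunogenicity end dates for the long-term and Part 1C-1 analyses, and state the same end date for Parts 1C-2, 2 and 3.
- Section 6.5.2: define censoring time and include this event.
- Section 6.4.6: exclude antibody results after that date from the main persistence summaries.
- Section 5.3: add the criterion to the Part 2 per-protocol subset.
- Section 6.1 safety periods: align them with Part 1A, or state why they differ.
- Keep the analysis regardless of off-study vaccination as a labelled sensitivity analysis.

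The cost is mainly wording. The schedules record non-study vaccinations throughout Parts 2 and 3, and the Part 1C safety calls ask about them. In Parts 1A and 1B, routine recording runs to 28 days after each injection, with later doses picked up in the Part 1A safety calls, so completeness of long-term dates should be checked. The statistical price is fewer evaluable late samples, possibly from a selected group, which is a further reason to show the sensitivity analysis alongside.
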